##### BI 1323495

BI 1323495 is a potent and highly selective inhibitor of NE. Taking into account the mode of action, the nature of the target, non-clinical findings, and the relevance of animal species and models, BI 1323495 is not considered a high-risk compound. Two compounds with the same mode of action as BI 1323495 have already been tested in phase I and II clinical trials with no relevant safety issues detected ([c21238478-05](#)).

The formation of active NE, together with two other neutrophil serine proteases (NSPs: Cathepsin G, Proteinase 3), is catalysed by Cathepsin C (CatC) in maturing neutrophil precursor cells in the bone marrow. A human genetic disease exists, Papillon-Lefèvre syndrome (PLS), in which patients completely lack functional NSPs (including NE) due to complete deficiency for CatC. The neutrophils of PLS patients upon activation are unable to release active NSPs, including NE. The phenotype of these patients can be looked at as a human model of a pharmacologically induced complete suppression of NE (and other NSPs). Despite this complete lack of functional neutrophil serine proteases, which may be expected to weaken the microbicidal capacity of neutrophils, the associated immunodeficiency in Papillon-Lefèvre syndrome patients is generally mild.

The target organs in the preclinical assessment of toxicity with BI 1323495 were the liver and kidney, and coagulation pathway in rodents, and as responsive organ, the immune system and coagulation pathway in the cynomolgus monkey.

Effects on the liver were indicated by increases in liver enzymes (Aspartate transaminase [AST], ALT, or GLDH), decreases in cholesterol and triglycerides, and an increase in total bilirubin in rats at 600 or 900 mg/kg/day. Biliary hyperplasia was observed in female rats given 900 mg/kg/day for 4-weeks. The liver findings were still present at the end of the 4-wk recovery period, but they were not seen in the 13-week toxicity trials although male rats achieved high exposures. The drug exposure was much higher in these animals than those expected in man and observed in the SRD trial 1405-0001.

*Risk mitigation and monitoring:* Although alterations are not specifically expected, liver function tests including total and direct bilirubin will be monitored as part of the standard safety laboratory assessments (see Section [5.2.3](#)). Subjects with impaired liver function will be excluded from participation in this trial.

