#### **5.2.3. Safety laboratory parameters**

For the assessment of laboratory parameters, blood and urine samples will be collected by the trial site at the time points indicated in the [Flow Chart](#) after the subjects have fasted for at least 10 h, except 4 h post dosing on Day 1 of SRD part and screening. For retests, at the discretion of the investigator or designee, overnight fasting is not required. The parameters that will be determined are listed in Tables [5.2.3: 1](#) and [5.2.3: 2](#). Reference ranges will be provided in the ISF, Section [10](#).

Manual differential white blood cell count or urine sediment examinations will only be performed if there is an abnormality in the automatic blood cell count or in the urinalysis, respectively.

Table 5.2.3: 1 Routine laboratory tests

Functional lab group	BI test name [comment/abbreviation]	A 	B 	C 	D 
Haematology	Haematocrit	X	X	--	X
	Haemoglobin	X	X	--	X
	Red Blood Cell Count/Erythrocytes	X	X	--	X
	White Blood Cells/Leucocytes	X	X	--	X
	Platelet Count/Thrombocytes (quant)	X	X	--	X
Automatic WBC relative	Neutrophils/Leukocytes; Eosinophils/Leukocytes; Basophils/ Leukocytes; Monocytes/Leukocytes; Lymphocytes/Leukocytes	X	X	--	X
Automatic WBC differential	Neutrophil, absol.; Eosinophils, absol.; Basophils, absol.; Monocytes, absol.; Lymphocytes, absol.	X	X	--	X
Manual differential WBC (if automatic differential WBC is abnormal and clinically relevant in the opinion of the investigator)	Neut. Poly (segs; Neutrophils Bands; Eosinophils/Leukocytes; Basophils/ Leukocytes; Monocytes/ Leukocytes; Lymphocytes/Leukocytes;				
Coagulation	Activated Partial Thromboplastin Time	X	--	--	--
	Prothrombin time	X	--	--	--
	INR (International Normalization Ratio)	X	--	--	--
	Fibrinogen	X	X	--	--
Enzymes	AST [Aspartate transaminase] /GOT	X	X	X	--
	ALT [Alanine transaminase] /GPT	X	X	X	--
	Alkaline Phosphatase	X	X	X	--
	Gamma-Glutamyl Transferase	X	X	X	--
	Creatine Kinase [CK]	X	X	--	--
	Creatine Kinase Isoenzyme MB [only if CK is elevated and clinically relevant in the opinion of the investigator]	X	X	--	--
Hormones	Thyroid Stimulating Hormone	X	--	--	--
Substrates	Glucose (Plasma)	X	X	--	--
	Creatinine	X	X	--	--
	GFR/ CKD-EPI	X	X	--	--
	Bilirubin, Total	X	X	--	--
	Bilirubin, Direct	X	X	--	--
	Protein, Total	X	X	--	--
	C-Reactive Protein (Quant)	X	X	--	--
	Cholesterol, total	X	--	--	--
Electrolytes	Triglyceride	X	--	--	--
	Sodium	X	X	--	--
	Potassium	X	X	--	--

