 A: parameters to be determined at Visit 1 and EOT

B: parameters to be determined at Visit 2 and 3 (for trial days and time points refer to [Flow Chart](#))

C: parameters to be determined at Visit 3 (for trial days and time points refer to Flow Chart)

D: parameters to be determined at Visit 2 (only for MD part)

 Microscopic examination if erythrocytes, leukocytes, nitrite or protein in urinalysis are abnormal in urine

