**6.7 BASELINE, TIME WINDOWS AND CALCULATED VISITS**

The baseline value is defined as the last measurement before administration of BI 1323495 in each treatment period.

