## **7.8.2      Laboratory data**

The analyses of laboratory data will be descriptive in nature and will be based on BI standards "Display and Analysis of Laboratory Data" ([9](#)).

Analyses will be based on normalised values, which means transforming to a standard unit and a standard reference range. The original values will be analysed if the transformation into standard unit is not possible for a parameter.

Descriptive statistics of laboratory values over time and for the difference from baseline (see [Section 6.7](#)) will be provided. Frequency tables of changes between baseline and last value on treatment with respect to the reference range will be presented.

Unscheduled measurements of laboratory data will be assumed to be repeat measurements of the most recent scheduled measurement (e.g. for follow-up or confirmation of a particular value). Therefore, unscheduled measurements will be assigned to the planned time point of the previous scheduled measurement. Descriptive statistics will be calculated by planned time point based on the worst value of the subject at that planned time point (or assigned to that planned time point).

Possibly clinically significant abnormal laboratory values are only those identified either in the Investigator's comments or at the Report Planning Meeting at the latest. It is the Investigator's responsibility to decide whether a lab value is clinically significant abnormal or not. Standard or project-specific rules for flagging clinically significant values in an automated manner will not be applied in this study.

Clinically relevant findings in laboratory data will be reported as baseline conditions (prior to first administration of study treatment) or as AEs (after first administration of study treatment) if judged clinically relevant by the investigator, and will be analysed as such.

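### Lipid change from baseline is confounded with fasting status: screening, the only pre-dose lipid sample, is exempt from the 10 h fast and the End of Trial sample is not

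*Protocol*

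**What the plan says.** Protocol Section 5.2.3 requires safety laboratory samples "after the subjects have fasted for at least 10 h, except 4 h post dosing on Day 1 of SRD part and screening". EOT is not among the exceptions.

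In Table 5.2.3: 1 the rows "Cholesterol, total" and "Triglyceride" are marked in set A and in no other set. The footnote gives the timing of that set: "A: parameters to be determined at Visit 1 and EOT". The flow charts for all three parts agree. Every scheduled safety draw between screening and EOT is set B, C or D, and none of these contains lipids.

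SAP 6.7 sets the reference point: "The baseline value is defined as the last measurement before administration of BI 1323495 in each treatment period". SAP 7.8.2 then plans "Descriptive statistics of laboratory values over time and for the difference from baseline", and adds: "Frequency tables of changes between baseline and last value on treatment with respect to the reference range will be presented". Neither document has a rule for fasting status in the analysis, or provides for recording it at screening.

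Protocol Section 1.4.2 lists "decreases in cholesterol and triglycerides" among the liver effects seen in rats at 600 or 900 mg/kg/day.

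**The concern.** Each subject has one lipid value before dosing and one after. The first is taken with no control over food intake and the second after at least 10 h without food. If food raises the analyte, the difference between the two falls with no drug effect. That is the direction of the rat finding, so the table could suggest an effect that is not there, or conceal a rise. With only one post-dose lipid value, no other scheduled sample can settle the question.

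Glucose, another meal-sensitive test, does not have this problem under the written rule. It is also in set B, so its baseline is a later pre-dose sample covered by the fasting requirement.

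**Working it through.** **1. Fasting rule, lipid draws and baseline side by side**

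| Visit | Lipids measured? | 10 h fast required? | Role in SAP 6.7 and 7.8.2 |
|---|---|---|---|
| Screening (Day -28 to -8) | Yes (set A) | No | Baseline, as the only pre-dose value |
| Later pre-dose safety draws | No (sets B, C) | Yes | None for lipids |
| EOT | Yes (set A) | Yes | The only post-dose value |

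In DDI Period 2 the screening value is again the only pre-dose lipid value available.

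**2. Possible size**

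The plan gives no figure to reproduce. Let r be the ratio of a fed to a fasted value in the same subject, and f the share of subjects fed at screening. With no drug effect, the geometric mean of EOT over screening is r^(-f), so the apparent change is r^(-f) - 1. Both r and f are assumptions. The ratio scale is used for convenience; the SAP tabulates differences, which move in the same direction.

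| r (assumed) | f = 0 | f = 0.25 | f = 0.5 | f = 1 |
|---|---|---|---|---|
| 1.0 | 0% | 0% | 0% | 0% |
| 1.1 | 0% | -2.4% | -4.7% | -9.1% |
| 1.2 | 0% | -4.5% | -8.7% | -16.7% |
| 1.3 | 0% | -6.3% | -12.3% | -23.1% |

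For example, 1/1.3 - 1 = -23.1%, and 1.2^(-0.5) - 1 = -8.7%. The two lipids need not share the same r.

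**3. What placebo removes**

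Planned placebo numbers are 3 x 2 + 3 x 1 = 9 in SRD (PM and EM) and 2 x 3 = 6 in MD. The apparent active-to-placebo difference is r^(-(fA - fP)) - 1, where fA and fP are the shares fed at screening in the active and placebo groups. Randomisation within dose groups makes fA and fP equal in expectation, and the shift is then zero. Chance imbalance remains possible in groups this small: with fA - fP = 0.25 and r = 1.2 it is -4.5%. The DDI part is open-label with a fixed sequence and no placebo, so step 2 applies there in full.

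**4. Which tables are affected**

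The on-treatment phase ends at the last relevant dose plus the residual effect period (SAP Tables 6.1: 1 and 6.1: 2).

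| Part | End of on-treatment phase | EOT window |
|---|---|---|
| SRD | Day 1 + 7 = Day 8 | Day 9 to 15 |
| MD | Day 11 + 7 = Day 18 | Day 19 to 21 |
| DDI Period 2 | Day 7 + 9 = Day 16 | Day 16 to 23 |

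EOT lipids are almost always follow-up values. The mismatch therefore falls on the difference-from-baseline tables and mostly stays out of the shift table, which uses the last on-treatment value.

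**The case against.** A reader might infer that the plan produces a lipid decrease by construction. The documents do not support that. Section 5.2.3 lifts the requirement at screening; it does not say that subjects attend fed. If all of them happen to fast, or the analyte does not respond to food, the shift is zero. A range that leaves out zero would be wrong.

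A reader might also infer that each dose group has only its own 1 to 3 placebo subjects as control. Protocol Sections 3.2 and 7.3.4 pool placebo across SRD dose groups, and SAP Table 6.1: 1 carries a single placebo label, so the control is larger and the shift largely cancels.

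The safety stake is also modest. The rat findings arose at exposures far above those expected in man and were not seen in the 13-week studies. The protocol's stated mitigation is liver function tests including bilirubin, and these have pre-dose draws in set B. No primary or secondary endpoint, stopping rule or escalation criterion specifically uses lipids.

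Finally, the fasting sentence is an imperfect guide to practice. Read literally, it also requires a 10 h fast for the MD set D draw 2 h after the Day 1 dose, which follows an 08:30 breakfast. That weakens any inference about how EOT samples will actually be taken.

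All of this stands, and it limits the size and reach of the problem. It does not remove the mismatch: by the written rule the two lipid samples are taken under different conditions, and nothing in the plan allows the difference to be identified or adjusted for.

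**Conclusion.** The concern holds as a minor weakness that is cheap to correct. The planned lipid difference from baseline is confounded with fasting status and may show a spurious decrease or hide a rise. The size cannot be determined from the documents: 0 to -23% under an assumed fed/fasted ratio of 1.0 to 1.3 and any share of subjects fed at screening. It matters most in the DDI part (14 planned subjects, no control). In SRD and MD the comparison with placebo largely removes it, apart from chance imbalance. The consequence is confined to descriptive safety tables, mostly of follow-up values. The conclusion rests on EOT samples being taken fasted, as Section 5.2.3 requires.

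**What to change.** Preferred: delete *and screening* from the exemption in Section 5.2.3, so that both set A draws follow a fast of at least 10 h. The cost is that subjects attend screening fasted. The MD post-dose set D draws should be reconciled with the same sentence in that edit.

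Alternative: add total cholesterol and triglyceride to a pre-dose morning blood draw on Day 1 (Period 1 in DDI), after the overnight fast and before any breakfast, and name that value as the lipid baseline. The flow charts show pre-dose draws at 07:00 in SRD and DDI and at 08:00 in MD. The 10 h rule must be applied to this draw explicitly. The DDI food restriction alone starts 10 h before the 09:00 dose, at 23:00, which is only 8 h before 07:00. SAP 6.7 would also need a stated exception for lipids in DDI, because it defines baseline separately for each treatment period. The cost is two routine assays per subject and a small blood volume counted towards the 400 mL limit.

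The Day -1 draw is not a suitable substitute. It is scheduled at 15:00 in SRD and DDI and at 17:00 in MD, so a 10 h fast would have to start at 05:00 or 07:00.

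For samples already collected, the SAP should state that lipid changes are read against pooled placebo in SRD and MD, and that in DDI they cannot be separated from fasting status at screening. This costs a few sentences.

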**Table 5.2.3: 1      Routine laboratory tests (cont.)**

Functional lab group	BI test name [comment/abbreviation]	A 	B 	C 	D 
Urinalysis (Stix)	Urine Nitrite (qual) Urine Protein (qual) Urine Glucose (qual) Urine Ketone (qual) Urobilinogen (qual) Urine Bilirubin (qual) Urine RBC/Erythrocytes (qual) Urine WBC/Leucocytes (qual) Urine pH	X X X X X X X X	X X X X X X X X	-- -- -- -- -- -- -- --	-- -- -- -- -- -- -- --
Urine sediment 	Only positive findings will be reported (for instance, the presence of sediment bacteria, casts in sediment, squamous epithelial cells, erythrocytes, leukocytes)				

 A: parameters to be determined at Visit 1 and EOT

B: parameters to be determined at Visit 2 and 3 (for trial days and time points refer to [Flow Chart](#))

C: parameters to be determined at Visit 3 (for trial days and time points refer to Flow Chart)

D: parameters to be determined at Visit 2 (only for MD part)

 Microscopic examination if erythrocytes, leukocytes, nitrite or protein in urinalysis are abnormal in urine

The tests listed in Table 5.2.3: 2 are exclusionary laboratory tests that may be repeated as required. The results will not be entered in the CRF/database and will not be reported in the CTR. Infectious serology is planned to be performed at screening only. Drug screening will be performed at screening and prior to first dose in each treatment period.

**Table 5.2.3: 2      Exclusionary laboratory tests**

Functional lab group	Test name
Drug screening (urine)	Amphetamine/MDA Barbiturates Benzodiazepine Cannabis Cocaine Methamphetamines/MDMA/XTC Opiates Phencyclidine Tricyclic antidepressants
Infectious serology (blood)	Hepatitis B surface antigen (qualitative) Hepatitis B surface antibody (qualitative) Hepatitis B core antibody (qualitative) Hepatitis C antibodies (qualitative) HIV-1 and HIV-2 antibody (qualitative) T-SPOT Syphilis test (RPR, TP antibody method)
Imaging test	Chest x-ray (For checking onset or history of tuberculosis)

To encourage compliance with alcoholic restrictions, a breath alcohol test will be performed prior to each treatment period, and may be repeated at any time during the trial at the discretion of an investigator or designee. The results will not be included in the CTR.

The laboratory tests listed in Tables [5.2.3: 1](#) and [5.2.3: 2](#) will be performed at the local laboratory of the trial site or/and at a CRO designated by the sponsor. Laboratory data will be transmitted electronically from the site to BI.

#### **5.2.4.      Electrocardiogram**

##### Recording

Twelve-lead resting ECGs (I, II, III, aVR, aVL, aVF, V1 - V6) will be recorded using a computerised electrocardiograph at the time points given in the [Flow Chart](#). Precise electrode placement will be marked with an indelible mark on the skin to allow reproducible placement throughout the trial.

To achieve a stable heart rate at rest and to assure high quality recordings, the site personnel will be instructed to assure a relaxed and quiet environment, so that all subjects are at complete rest.

All ECGs will be recorded for a 10 sec duration after subjects have rested for at least 5 min in a supine position. ECG recording will always precede all other trial procedures scheduled for the same time (except for blood drawing from an intravenous cannula that is already in place) to avoid compromising ECG quality.

ECGs will be recorded as single ECGs or as triplicate ECGs (i.e. three single ECGs recorded within 180 sec) as indicated in the Flow Chart.

ECGs may be repeated for quality reasons for instance due to alternating current artefacts, muscle movements, or electrode dislocation. For repetition within triplicate ECGs the time window of 180 sec applies as well. The repeat ECGs are assigned to the respective scheduled time point.

Additional (unscheduled) ECGs may be recorded for safety reasons. These ECGs are assigned to the prior scheduled time point in the sponsor's database.

##### Storing

All ECGs will be stored as print out.

##### Evaluation

All local ECGs will be evaluated by the investigator or a designee.

For the inclusion or exclusion (see Section [3.3](#)) of a subject and for the assessment of cardiac safety during the trial, the QT and QTcF values generated by the computerised ECG system or their manual corrections by the investigators will be used.

Abnormal findings will be reported as AEs (during the trial) or baseline conditions (at screening) if judged clinically relevant by the investigator.

Any ECG abnormalities will be monitored carefully and, if necessary, the subject will be removed from the trial and will receive the appropriate medical treatment.

### **5.2.5. Other safety parameters**

Not applicable.

### **5.2.6. Assessment of adverse events**

#### **5.2.6.1. Definitions of adverse event**

##### **5.2.6.1.1. Adverse event**

An adverse event (AE) is defined as any untoward medical occurrence in a patient or clinical investigation subject administered a medicinal product and which does not necessarily have to have a causal relationship with this treatment.

An AE can therefore be any unfavorable and unintended sign (including an abnormal laboratory finding), symptom, or disease temporally associated with the use of a medicinal product, whether or not considered related to the medicinal product.

The following should also be recorded as an AE in the CRF and BI SAE form (if applicable):

- Worsening of the underlying disease or of other pre-existing conditions
- Changes in vital signs, ECG, medical examination, and laboratory test results, if they are judged clinically relevant by the investigator.

If such abnormalities already pre-exist prior to trial inclusion, they will be considered as baseline conditions and should be collected in the eCRF only.

##### **5.2.6.1.2. Serious adverse event**

A serious adverse event (SAE) is defined as any AE which fulfils at least one of the following criteria:

- Results in death
- Is life-threatening, which refers to an event in which the patient was at risk of death at the time of the event; it does not refer to an event that hypothetically might have caused death if more severe,
- Requires inpatient hospitalisation
- Requires prolongation of existing hospitalisation
- Results in persistent or significant disability or incapacity
- Is a congenital anomaly/birth defect
- Is deemed serious for any other reason if it is an important medical event when based upon appropriate medical judgment which may jeopardize the patient and may require medical or surgical intervention to prevent one of the other outcomes listed in the above definitions. Examples of such events are intensive treatment in an emergency room or at home for allergic bronchospasm, blood dyscrasias or convulsions that do not result in hospitalization or development of dependency or abuse

Proprietary confidential information © 2021 Boehringer Ingelheim International GmbH or one or more of its affiliated companies

The following events will be handled as ‘deemed serious for any other reason’. An AE that possibly leads to disability will be ‘deemed serious for any other reason’ and reported as an SAE.

#### 5.2.6.1.3. AEs considered ‘Always Serious’

Cancers of new histology and exacerbations of existing cancer must be classified as a serious event regardless of the time since discontinuation of the trial medication and must be reported as described in [5.2.6.2](#), subsections ‘AE Collection’ and ‘AE reporting to sponsor and timelines’.

In accordance with the European Medicines Agency initiative on Important Medical Events, Boehringer Ingelheim has set up a list of further AEs, which, by their nature, can always be considered to be ‘serious’ even though they may not have met the criteria of an SAE as defined above.

The latest list of ‘Always Serious AEs’ can be found in the electronic data capture (eDC) system, an electronic data capture system which allows the entry of trial data at the trial site. These events should always be reported as SAEs as described above.

#### 5.2.6.1.4. Adverse events of special interest

The term adverse events of special interest (AESI) relates to any specific AE that has been identified at the project level as being of particular concern for prospective safety monitoring and safety assessment within this trial, e.g. the potential for AEs based on knowledge from other compounds in the same class. AESIs need to be reported to the sponsor’s Pharmacovigilance Department within the same timeframe that applies to SAEs, please see section [5.2.6.2.2](#).

The following are considered as AESIs:

